2 METHODOLOGY OF THE STUDY

2.1 DESIGN

This is a prospective analytical observational experimental pilot study that aims to analyse the substances of particular concern and endocrine disruptors detected in saliva, released by conventional dental devices, before and after the intervention. They will therefore be paired samples, where the control group will be the same subject, minimising the independent variables: saliva pH, microbiome, salivary flow, habits, occlusal wear, erosion by external agents and saliva.

Saliva sampling shall be carried out in accordance with the conventional protocol RD 1716/2011. The saliva containers shall comply with the requirements of the ISO 6717:2021 standard. They shall be packaged and transported according to the protocol Order JUS/1291/2010 of 13 May. All samples shall be identified with the number assigned to the volunteer, time, material and type of manufacture (processed, machined or printed), and shall be sent to the Chemical Institute for Energy and Environment (IQUEMA). University of Cordoba, where they will be analysed by the SAC group, for subsequent statistical treatment and interpretation.

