2.6 DESCRIPTION OF THE STUDY

2.6.1 VOLUNTEER RECRUITMENT:

The study groups will be formed in accordance with the requirements and inclusion criteria. Each of the subjects will be informed of the purpose and methodology of the project by means of an information document for the volunteer (Appendix II) and must sign the informed consent form provided for this purpose (Appendix III); they may withdraw from participation at any time. The data of the participants will be stored in a clinical history with an individual key number, in accordance with the regulations contained in the current Organic Law 3/2018, of 5 December, on the Protection of Personal Data.

Appointments will be made as follows:

APPOINTMENT 1: A conventional computerised clinical history is taken of the patient, in which data is collected on general health, orofacial and nutritional habits and hygiene. We explain in detail what the treatment consists of: Michigan type relaxation splint (device to prevent tooth wear due to bruxism). Each intervention is governed by scientific and deontological criteria, respecting all the ethical rules of research. The following is a detailed description of the study, its duration and methodology. The four moments of saliva collection will be explained: before, during, and 3 and 6 months after placement, as follows:

-Time 0: the day of the appointment, before the intervention.

-Step 1: On the day of the appointment, device placement.

-Time 2: 3 months after device placement.

-Time 3: 6 months after treatment.

Information and informed consent will be provided.

APPOINTMENT 2: Preparation and taking of models for the Michigan type splint according to the conventional protocol for this treatment.

APPOINTMENT 3: The models will be assembled in the articulator to send and request the making of the splint, specifying whether it is injected or printed.

APPOINTMENT 4: A saliva sample is taken in the device for this purpose. After checking for proper fit and retention, the occlusal adjustments will be made with a handpiece and conventional acrylic and polishing burs. After completion of the procedure, a new saliva sample shall be taken. The samples shall be identified with the patient's assigned code and stored according to conventional standards. An appointment will be made after 6 months to continue with the study and in accordance with the check-up times for correct oral health.

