APPOINTMENT 5: The intraoral check-up will be carried out, checking the intraoral health and the state of the splint, with the pertinent adjustments, according to conventional protocol. A new saliva sample will be taken. The patient will be seen after 3 months.

APPOINTMENT 6: The intraoral check-up will be carried out, checking the intraoral and splint health status, with its pertinent adjustments, according to conventional protocol. A new saliva sample will be taken. The sample collection period for this subject will end.

Prior to this, the substances released by the specific material used to make the devices will be identified in the laboratory. The reason for this is the highly dynamic nature of the dental materials market. For this purpose, the solutions will be analysed by liquid chromatography coupled to a mass spectrometer (LC-HRMS). The identification of the compounds present will be based on a non-directed suspect screening approach, comparing the results obtained in the analyses with those already existing for the

RESEARCH PROTOCOL

compounds included in the

list of suspects. This list shall be compiled on the basis of information gathered during the literature review, among other sources. Thus, it shall include from compounds whose presence is expected such as those indicated by the manufacturer, to emerging compounds that could be present due to storage conditions, use, etc. For the identification, statistical and chemometric techniques will be used to establish the correlation between the analytical signals obtained in the LC-HRMS and the information (e.g. masses, structure, mass spectra, etc.) available in bibliography and publicly available spectrophotometric libraries (e.g. Mass Bank). In a second phase, the compounds identified in the first stage will be prioritised according to their level of identification, frequency of detection, toxicity (if known) and availability of analytical standards. Finally, quantification of these compounds will be carried out (figure 1).

[figure not shown]

Figure 1: Timeline *In vitro* study of acrylic-based dental materials: Resting and weathering phase leaching, identification and quantification of released substances EDs and SEP. SAC innovative research group at the University of Córdoba (Spain) that belongs to the Institute of Fine Chemistry and Nanochemistry (IUNAN).

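### Saliva samples reach the laboratory identified by sampling time and splint type, an avoidable risk of expectation bias when compounds are identified

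*Protocol*

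**What the plan says.** Section 2.1 (Design) sets the identification rule for the saliva samples: "All samples shall be identified with the number assigned to the volunteer, time, material and type of manufacture (processed, machined or printed". The same paragraph sends them to the university's supramolecular analytical chemistry (SAC) group for analysis.

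Section 2.6.1, Appointment 4, is shorter: "The samples shall be identified with the patient's assigned code and stored according to conventional standards". Two samples are taken at that appointment, one before the splint is adjusted and one afterwards: "After completion of the procedure, a new saliva sample shall be taken". Appointment 1 lists the four collection times as "before, during, and 3 and 6 months after placement".

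Section 2.6 describes the laboratory method, starting with the splint materials in vitro: "The identification of the compounds present will be based on a non-directed suspect screening approach". It adds: "For the identification, statistical and chemometric techniques will be used to establish the correlation between the analytical signals obtained". The compounds found are then ranked by level of identification, detection frequency, known toxicity and availability of standards, and finally quantified. The Figure 1 caption names the SAC group for this in vitro phase. The text after the figure says that saliva is treated once the candidate compounds are known, and that the in vitro methodology is used again.

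Section 1.4 makes identification in saliva (objective 2), the contrast of in vitro with saliva results (objective 4), and the relation to manufacture, stage and time (objective 5) explicit aims. Section 2.4 plans 15 volunteers with injected and 15 with printed splints.

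**The concern.** The study makes two main contrasts: before against after placement, and injected against printed. The rule in section 2.1 attaches the answer to both to every sample sent for analysis. The group that receives the samples will already know what the splint materials released in vitro.

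If any decision that a compound is present in a sample involves judgement, a reader who knows that a sample follows placement of a given splint type may accept a borderline signal. The same signal might be set aside in a sample taken before placement. That error would differ between the groups and times being compared, so it would not average out. Objective 4 is the most exposed: if in vitro expectation guides identification in saliva, some of the agreement between the two phases is built in. Section 1.2 itself stresses that these substances come from many everyday sources and are hard to attribute to a dental device, which makes uncertain signals more plausible.

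**Working it through.** The protocol gives no figure to reproduce here. The check sets the sections side by side and counts the samples affected.

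**1. What the laboratory is given.** Section 2.1: volunteer number, time, material and manufacture, for all samples.

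**2. What it already knows.** Section 2.6: the in vitro results come first and inform the treatment of saliva. The SAC group is named for saliva in section 2.1 and for the in vitro phase in the Figure 1 caption.

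**3. Where judgement could enter.** Section 2.6 describes matching signals to a suspect list and to spectral libraries, then ranking by level of identification. The ranking orders compounds and not individual samples. No section describes a sample-by-sample decision by an analyst. Judgement at that step is therefore an assumption, which the text neither states nor excludes.

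**4. Which results are exposed.** Identification in saliva (objective 2), the in vitro contrast (objective 4) and the relation to manufacture and time (objective 5). Quantification against standards (objective 3) is less exposed.

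**5. How many samples.** Inputs: 30 volunteers in two groups of 15 (section 2.4) and four samples each (section 2.6.1).
- Total: 30 x 4 = 120.
- By manufacture: 15 x 4 = 60 injected and 60 printed.
- By time: 30 before, 30 on placement day, and 30 x 2 = 60 later.

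**6. How much one call weighs.** If detection is analysed as yes/no, one changed call in one group at one time moves that group's detection frequency by 1/15 = 6.7 percentage points. In the 30 volunteers together it moves it by 1/30 = 3.3 points. This shows leverage only. How many calls might change, if any, cannot be obtained from the document.

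**7. The two identification statements.** Section 2.6.1 names the patient's code. Section 2.1 names the volunteer's number and three further items. The first is contained in the second, and both can be followed at once. The code alone could not separate the two samples taken at Appointment 4, so the shorter statement cannot be a complete rule.

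**The case against.** The case against is substantial. Section 2.1 says what samples are identified with. It does not say that the items are printed on the tube, or what the person making the identification sees. The method rests on instrument signals, libraries and chemometrics, and no subjective step is documented. A masking statement in the unavailable part of the protocol between sections 2.1 and 2.3.4 cannot be excluded. The study is a 30-person pilot. Masking could also leak, because a group that knows each material's in vitro profile might infer splint type from a sample's contents.

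These points limit the finding to a risk, but they do not remove it. An accompanying form seen by the analysts would expose the contrasts just as a tube label would. The text at hand gives no analytical reason why the laboratory needs time or manufacture to process a sample. A pilot meant to lay the basis of a protocol is a good place to set the rule. Possible leakage makes masking imperfect, but it is no reason to hand over the information directly.

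A reader might also infer a contradiction between sections 2.1 and 2.6.1. The text does not support this: Appointment 4 does not say that the code is the sole identifier, and it reads as shorthand for the fuller rule.

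A reader might likewise take the manufacture categories in section 2.1, which do not match the injected and printed groups of section 2.4, as a source of misclassification. Annex IV records manufacture as injected or printed, so nothing of the kind follows. It is a wording slip and does not bear on bias.

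**Conclusion.** The point holds as a cheap improvement against a possible bias. Section 2.1 positively fixes an identification rule that makes both study contrasts available to the laboratory for all 120 planned samples, at a time when it knows the in vitro results. The exposure concerns objectives 2, 4 and 5, and quantification less.

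A reader might infer that the identification results will be biased, or that the laboratory is shown to be unmasked. Neither is supported. The conclusion rests on two assumptions: that some identification decisions leave room for judgement, and that no masking rule stands in the part of the protocol not available here. The size of any bias cannot be derived.

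**What to change.** In section 2.1, replace the identification rule with the following, and use the same wording at Appointment 4 in section 2.6.1:
- Send samples to the laboratory under a neutral random sample ID only.
- Hold the key (volunteer, time 0 to 3, injected or printed) outside the laboratory until identification and quantification are locked.
- Randomise run order within batches.
- Analyse each volunteer's time 0 and time 1 samples in the same batch. They come from one appointment, so 30 x 2 = 60 of the 120 samples can be paired in this way without waiting for a later visit.

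The cost is a key file to keep and reconcile after the laboratory data are locked. No extra samples, assays or visits are needed, and a unique sample ID also separates the two same-day samples.

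Two limits should be acknowledged in the text. If samples are run as they arrive, the later time points stay partly unmasked by batch order. Holding earlier samples would avoid this, but the protocol gives neither the timing of the saliva runs nor the stability of the analytes, so the storage cost cannot be stated. Sample contents may also still hint at splint type.

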2.3.4 STATISTICAL DATA CONTROLLER

[name] [name] (Methodological and Statistical Advisory Group, Department of Medicine, Faculty of Biomedical and Health Sciences), European University of Madrid.

2.4 POPULATION AND CALCULATION OF THE SAMPLE.

The sample will be obtained from patients who are registered in the database of the Polyclinic of the European University of Madrid, who request a Michigan type splint for the treatment of bruxism, made of acrylic, made in two of the usual ways: printed or injected, in accordance with the inclusion and exclusion criteria shown in Appendix I. As the samples were treated with an innovative methodology in the field of dentistry, such as super solvents, this was a pilot study in which two groups of 15 participants each were formed, depending on the manufacturing process of the splint: injected or printed, totaling 30 volunteers.

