1.4 OBJECTIVES

There is no evidence of release of substances of particular concern, or endocrine disruptors released from Michigan type acrylic occlusal splints.

General objectives: To describe and quantify the values of substances of very high concern (SVHC) or endocrine disruptors (ED) released from printed or injected acrylic Michigan type splints.

Specific objectives:

1. To identify the SEPs and EDs released by Michigan-type splints made by injection or *in vitro* impression technique, simulating oral environment and wear.
2. Identify SEPs and EDs in saliva released from printed or saliva-injected acrylic Michigan type splints before, during and after insertion in the mouth.
3. To quantify the levels of SEP and ED in saliva released from printed or injected acrylic Michigan type splints in saliva before, during and after insertion in the mouth.
4. Contrast the results obtained in the laboratory test with those recorded in the saliva samples of the *in vivo* study.

5. Relate the results to the manufacturing process, stage of exposure, time, habits and individual characteristics of each volunteer.

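### No allocation method is stated for the injected and printed groups and only unadjusted two-group tests are planned, so the manufacturing contrast in Objective 5 is open to systematic confounding

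*Protocol*

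**What the plan says.** Section 2.4 recruits clinic patients "who request a Michigan type splint for the treatment of bruxism, made of acrylic, made in two of the usual ways: printed or injected", and states that "two groups of 15 participants each were formed, depending on the manufacturing process of the splint", 30 volunteers in all. Section 2.6.1 adds only that "The study groups will be formed in accordance with the requirements and inclusion criteria"; the criteria in Annex I do not mention manufacture. At Appointment 3 the models go to the laboratory to "send and request the making of the splint, specifying whether it is injected or printed". This comes after the clinical history of Appointment 1, which covers health, nutrition and hygiene. The text does not mention a random list, concealment, or who chooses the type and on what grounds.

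The design section (2.1) says "This is a prospective analytical observational experimental pilot study" and makes each subject their own control for the before/after comparison. Specific objective 5 (section 1.4) is to "Relate the results to the manufacturing process, stage of exposure, time, habits and individual characteristics of each volunteer". The variable list in 2.6.1 names type of manufacture as an independent variable.

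For quantitative variables, section 2.8 names Student's t-test or the Mann-Whitney test, with significance at 0.05. It does not say whether raw concentrations or changes from Time 0 are compared. The only model it names is a logistic regression for seroprevalence, which this study does not measure.

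**The concern.** Pairing answers whether saliva changes after the splint is placed. Manufacture varies between people, so pairing protects that contrast only if the Time 0 value enters the analysis, and section 2.8 does not say that it does.

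The protocol itself supplies the likely confounders. Section 1.2 says that environmental, nutritional and hygienic sources make it very hard to trace a substance to a dental device. Annex IV records residence, reflux, three drug classes and hours of exposure. If one type is ordered more often for some kinds of volunteer, or in one part of the recruitment period, a printed-versus-injected difference could not be credited to manufacture. The study is meant to lay the foundations of a later protocol, so a misleading contrast could be carried forward.

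**Working it through.** **The plan's own figure.** 15 + 15 = 30, which is consistent. No effect size, SD or power is given, so nothing else can be reproduced.

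**Which objectives depend on allocation.**

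| Objective (1.4) | Comparison | Depends on allocation? |
|---|---|---|
| 1 | laboratory only | no |
| 2, 3 | same volunteer, before, during and after | no |
| 4 | laboratory against saliva | not in itself |
| 5, manufacture | different volunteers, 15 against 15 | yes |

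**Size of the error if Time 0 is ignored.** The documents give no confounder prevalence or effect, so these are assumptions: a background exposure differs by 30 percentage points between the groups and shifts log concentration by 0.5 to 1 SD.

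- Bias b = 0.30 × 0.5 = 0.15 SD, up to 0.30 × 1 = 0.30 SD.
- Standard error of the group difference, in SD units: √(2/15) = 0.365.
- Noncentrality: b / 0.365 = b × √7.5, with 28 degrees of freedom, two-sided 5% (section 2.8 does not state sidedness).

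| Bias (SD) | Noncentrality | Rejection with no true effect |
|---|---|---|
| 0 | 0 | 5.0% |
| 0.15 | 0.41 | 6.8% |
| 0.20 | 0.55 | 8.3% |
| 0.30 | 0.82 | 12.5% |

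A simulation with a binary confounder gave 8.0% at 0.20 SD and 12.4% at 0.30 SD. Under random allocation it gave 4.9% to 5.1%.

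**What the Time 0 sample can do.** Suppose the background difference is stable and additive on the analysis scale.

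- Comparing changes from Time 0 gives b − b = 0. In a simulation with a 30-point gap, a 1 SD effect and an assumed within-subject correlation of 0.5, type I error was about 11% on raw values and 5.0% on changes.
- Using Time 0 as a covariate leaves b × (1 − r), where r is the within-group correlation of Time 0 with the later value. For b = 0.30, this is 0.30 × 0.5 = 0.15 SD at r = 0.5, and 0.30 × 0.2 = 0.06 SD at r = 0.8. It therefore removes most of the difference when r is above 0.5.

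Neither method removes factors that change during follow-up, such as calendar period, or that alter release itself, such as hours of wear.

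**What randomisation can do at this size.** For a trait with 50% prevalence, chance alone gives a gap of at least 3 of 15 (20 points) in 36% of randomised studies, at least 4 of 15 in 20%, and at least 5 of 15 in 10%. An unrestricted list gives exactly 15:15 with probability 14%, so blocks are needed to hold the planned split.

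**The case against.** The strongest reply has four parts.

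- **The text is silent; it does not say that allocation is non-random.** The 2.4 wording defines the two groups, and "specifying whether it is injected or printed" on an order form would read the same under a random list. This stands. A reader might infer that the protocol declares a non-random choice, but it does not. The supportable statement is that no method is given, and how participants enter comparison groups is a matter for the protocol itself.
- **The paired design helps.** Each volunteer has a Time 0 sample, and using it cancels stable background. This also stands, so it would be wrong to say that pairing is no use for this contrast. But section 2.8 does not commit to using it, and wear time and recruitment date would remain.
- **The aim is modest.** The general objective is descriptive, and Objective 5 relates results to many factors at once without a causal claim. This stands, and it keeps the point to one contrast. But the study is built as 15 against 15 and plans two-group tests, so readers will read the result as a comparison of processes.
- **Covariates are recorded.** Residence, age, medication and exposure hours are collected. With 15 per group, adjusting for many of them at once is not reliable, and section 2.8 names no model for concentrations.

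**Conclusion.** The point holds for the between-subject manufacturing contrast in Objective 5 and does not touch the before/after objectives. With no stated allocation method and only unadjusted tests, that contrast is open to systematic confounding. For assumed biases of 0.15 to 0.30 SD on raw values, type I error would be about 7% to 12.5% instead of 5%. These sizes illustrate the risk and are not estimates.

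Two stronger readings are not supported. A reader might take a larger bias, such as 0.5 SD, which would give 26%; nothing in the documents suggests it, and it lies outside the range that the assumptions above produce. A reader might also conclude that a random list would remove confounding outright. It removes systematic bias in expectation, while chance imbalance stays common with 15 per group. It also cannot separate manufacture from resin or polymerisation type if these go with the process.

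**What to change.** 1. **Section 2.8.** Compare injected with printed on post-placement concentrations (log scale if skewed), adjusted for the volunteer's own Time 0 value. Where groups were not randomised, show the comparison of changes from Time 0 beside it, because covariate adjustment leaves part of a stable difference. This costs nothing, as the sample is already taken.
2. **Section 2.4 and Appointment 3.** For volunteers not yet allocated and suitable for either usual type, allocate 1:1 from a concealed permuted-block list, held by the statistics group and opened when the order is placed. N stays at 30. The costs are an update to the consent and the design description, and that volunteers who insist on one type stay outside the randomised comparison.
3. **If groups were already formed otherwise.** This may well be so: 2.4 is written in the past tense and 2.5 expected recruitment to end in January 2024. State how the type was chosen, keep the Time 0 adjustment, and report the contrast as an exploratory association.
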